Patients 18 years or older who have undergone surgical evacuation of a subdural hematoma and have a significant residual hematoma status post-surgery or who develop a recurrent subdural hematoma.
2. Minimal symptoms such as headache, altered mental status, or mild neurological deficit only
3. Ability to understand and sign written informed consent by patient or LAR

If any of the following criteria are met, the individual will be excluded from participation:

1. Significant midline shift and/or neurologic symptoms requiring urgent decompression.
2. Common carotid stenosis of over 50%.
3. Significant contraindication to angiography (eg. kidney failure, difficult anatomy).

4. SDH related to underlying condition

Groups:

1. Embolization Only
 - a. Patients with new chronic or acute SDH with minimal symptoms only, or who are poor surgical candidates (dual antiplatelet therapy or systemic anticoagulation, ASA Class 4 or greater)
2. Embolization + Standard of Care Evacuation
 - a. Patients with chronic or acute SDH who failed conventional surgery at any point needing additional intervention, not requiring urgent evacuation
 - b. Recurrent SDH
3. Medical Management (Historical Cohort)
4. Surgery Alone (Historical Cohort)

Study Procedure

Middle meningeal artery embolization is ideal for patients with minimal symptoms or that are poor surgical candidates due to the need for continued anticoagulant or antiplatelet therapy. For patients who meet inclusion criteria, MMA embolization as an adjunct treatment will be offered. For patients that are medically managed, they will undergo MMA embolization to prevent growth or recurrence of the hematoma and have standard imaging follow up. For patients that require evacuation of the hematoma due to size or symptoms, they will undergo standard of care surgery via burr hole or craniotomy at the treating neurosurgeon's discretion and then at a later date during the same hospitalization receive MMA embolization. These patients may have already had multiple surgical evacuations with recurrence of the hematoma.

Once consented and enrolled, patients will undergo MMA embolization in the neuro-angiography suite via selective MMA catheterization and embolization with 150-250 micron polyvinyl alcohol (PVA) particles. The neurointerventional radiology department at BJH is a high volume center. Physicians and staff are experienced in neurovascular embolization for a variety of indications.

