Middle meningeal artery embolization is a minimally invasive angiography procedure completed either under general anesthesia or conscious sedation (per preference of the performing physician) with use of fluoroscopy. Access is obtained through the femoral or radial artery and a catheter is advanced to the MMA. Polyvinyl alcohol particles are then injected to seal off this portion of the artery and prevent any further blood flow into the subdural hematoma. All catheters are then removed and hemostasis is obtained at the access site.

Patients will be followed post-procedure for 90 days to track any complications or recurrence/persistence of the subdural hematoma. Further treatment following standard of care will be offered if the patient develops worsening symptoms or presents with radiographic recurrence or persistence of the subdural hematoma.

A head CT, NIHSS, and modified Rankin Score will be repeated on the following schedule. These non-invasive procedures are detailed in the consent:

- Pre-Procedure
- 30 days (± 7) post procedure
- 90 days (± 10) post procedure

Data Points

Patient demographic data including but not limited to age, sex, race, comorbidities, previous neuro history, and relevant medical history will be gathered from Epic and Clindesk. Pre-procedure information gathered about the current admission include the use of anticoagulants, date of presentation with the SDH, size and hemisphere of SDH, neurologic presenting symptoms, head CTs, and neuro exams, including mRS and NIHSS.

Post-procedure data gathered include the time to embolization, time to follow up, procedural complications, neuro exam results, head CTs and angiography images. Date of surgery and need for surgical removal of recurrent hematoma will be documented if relevant.

The modified Rankin Score (mRS) is a well-established scale used to classify outcomes on a 0 to 6 point scale where outcome is classified as: 0- no neurological deficits, 1-no significant disability, 2- slight disability, 3-moderate disability (requires assistance with activities of daily life, but able to walk unassisted), 4-moderately severe disability (requires assistance in activities of daily life and unable to walk unassisted), 5-severe disability (bedridden, incontinent), or 6-deceased.

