The National Institutes of Health Stroke Scale (NIHSS) is an objective measure of impairment caused by a stroke. Eleven items are evaluated, with a potential score ranging from 0 to 42, with a higher score indicating more impairment.

Privacy/Data Protection

Patients will be assigned a unique study identification number at the time of consent. This number will link to identifying protected health information in a separate locked database accessible only to relevant research team members. Clinical study data will be entered into a secure database on RedCap under the study ID number to maintain patient data confidentiality.

Screening:

Study ID	MRN	Last Name	First Name	Admit Date	Enrolled Y/N	Date Consent Signed	Signed By Patient/ LAR	Exclusion

Initial Data:

Study ID	Birth Year	Sex	Race	(relevant comorbidities)	Use Anticoagulant y/n	Name of Med (aspirin, warfarin)	Procedure Date	Presenting neuro symptoms

Any neuro history	NIHSS Presentation	Baseline mRS	Size of SDH at Presentation	Laterality of SDH Left Right bilateral	Procedural Complications	

Follow up:

Study ID	Date of Follow Up	Time Point (30, 90 days)	NIHSS	mRS	Size of SDH at follow up	Neuro Deficit

Analysis

Endpoints

Two primary endpoints will be analyzed, related to the two main aims of the study. Aim 1 is to establish if middle meningeal artery embolization is more effective than observation alone at preventing recurrence of subdural hematoma. Aim 2 is to determine if adding on middle meningeal artery embolization reduces the need for further surgery in patients that initially undergo evacuation. The number of patients that experience a recurrent or refractory subdural hematoma will be compared, as well as the number of patients in each group that require surgery after undergoing embolization.

Primary Endpoints:

Recurrent or progressive SDH
Secondary surgical evacuation required

Secondary Endpoints:

Change in size of SDH at follow up
Procedure-related complications
New neuro deficit
NIHSS/mRS at follow-up intervals

Statistical Analysis

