Statistical comparisons will be made for the number of patients that experience a recurrent or refractory subdural hematoma, as well as the number of patients in each group that require evacuation surgery after undergoing embolization, an indication that the embolization procedure failed. These primary endpoints will be compared with simple t-test. The secondary endpoint of the change in the size of the subdural hematoma on radiographic imaging will be analyzed by repeated measures ANOVA. Change in score on NIH Stroke Scale pre and post embolization will be compared to determine the functional outcome of the procedure. For a safety analysis, the rate of procedure-related complications between embolized patients and surgical controls will be compared by t-test. Rankin Score at the follow up intervals will be compared with a Chi Square analysis.

Safety Monitoring Plan

Research will be performed according to protocols approved by the Institutional Review Board at Washington University in St. Louis School of Medicine. An application to the IRB is currently pending.

Patients with subdural hematoma present with symptoms including confusion or altered mental status, decreased consciousness, weakness or numbness on one side of the body, headache, seizure, and difficulty with speech, swallowing, or walking.

During this study, assessment of medical history and physical examination will be performed at baseline and at stated follow up intervals to ascertain neurologic status, change in functional baseline, and occurrence of any AEs. Prior to interventional procedures, patients have coagulation tests performed to assess risk of bleeding. If the patient has an allergy to iodinated contrast, they will receive standard pre-medication. During the embolization procedure, patients undergo continuous vital sign monitoring and are assessed frequently by a dedicated, ACLS-certified procedural nurse. The patient will be monitored as an inpatient in the neuroICU or stepdown unit for a minimum of 24-48 hours after the procedure.

Adverse Events

An adverse event (AE) is any untoward medical occurrence in a subject during participation in the clinical study or with use of the experimental agent being studied. An adverse finding can include a sign, symptom, abnormal assessment (laboratory test value, vital signs, electrocardiogram finding, etc.), or any combination of these.

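### The functional outcome rests on pre/post NIHSS change, which has no value or rule for patients who die, so that analysis describes survivors only

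*Combined protocol and SAP*

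**What the plan says.** All references are to the combined protocol and SAP.

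- **Statistical Analysis** gives the functional conclusion to one measure: "Change in score on NIH Stroke Scale pre and post embolization will be compared to determine the functional outcome of the procedure". It names no test, time point, comparator or summary statistic for this comparison, and no rule for deaths or missing scores.
- **Data Points** says the NIHSS "is an objective measure of impairment caused by a stroke", "with a potential score ranging from 0 to 42, with a higher score indicating more impairment". No value is set for death.
- **Data Points** also describes the mRS, in terms of disability and daily activities. Its top levels are "5-severe disability (bedridden, incontinent), or 6-deceased".
- **Statistical Analysis** then says: "Rankin Score at the follow up intervals will be compared with a Chi Square analysis". It does not link this test to the functional conclusion.
- **Endpoints** lists NIHSS and mRS together as one secondary endpoint. Mortality is not a listed endpoint.
- **Study Procedure** schedules both scales before the procedure and at 30 and 90 days.
- **Groups** allows the embolization-only group to take "Patients with new chronic or acute SDH with minimal symptoms only, or who are poor surgical candidates". ASA Class 4 or greater is one of the examples given of a poor surgical candidate.

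**The concern.** A change score needs two measurements. A patient who dies before day 30 has no post-procedure NIHSS at all. One who dies between the two visits has a day-30 change but no day-90 change. With no death rule, an ordinary pre/post comparison can use only patients who are alive and assessed, so the worst outcome is absent from the analysis that is meant to settle function.

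Some deaths within 90 days are foreseeable. The Background refers to mortality from this disease, Groups gives patients with severe systemic illness a route in, and Risks mentions life-threatening complications of the procedure.

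There is also a mismatch of labels. The plan calls the NIHSS a measure of impairment but uses it to judge function. The scale that it describes in functional terms, and that has a level for death, does not carry the conclusion. If the two scales disagreed, the text as written would favour the one that leaves deaths out.

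**Working it through.** **The plan's own figure.** The plan gives no expected NIHSS value, change, SD or mortality, so there is no figure to reproduce. The check is a comparison of sections followed by an illustration.

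**Comparison of sections**

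| Question | NIHSS change | mRS |
|---|---|---|
| Value for death | None (range 0 to 42) | 6 |
| Described in the plan as | Impairment | Disability and daily activities |
| Given the functional conclusion | Yes | No |
| Planned test | Not named | Chi-square |
| Deaths counted if followed as written | No | Yes, if recorded as 6 |

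**Illustration: inputs**
- N = 200 embolized patients (Participants).
- Worst NIHSS = 42 (Data Points).
- Assumed: baseline NIHSS b = 2 and mean survivor change s = -1.
- Assumed: mortality m of 2%, 5%, 10% or 15%.
- Assumed for the bound: each death is scored 42. The plan contains no such rule.

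**Formulas**
- Survivors only: mean change = s, whatever the value of m.
- Deaths scored 42: mean change = (1 - m) × s + m × (42 - b).
- With the inputs above: (1 - m) × (-1) + m × 40 = -1 + 41m.

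| Mortality | Deaths of 200 | Survivors analysed | Survivor-only mean | Deaths scored 42 |
|---|---|---|---|---|
| 2% | 4 | 196 | -1.0 | -1 + 0.82 = -0.18 |
| 5% | 10 | 190 | -1.0 | -1 + 2.05 = +1.05 |
| 10% | 20 | 180 | -1.0 | -1 + 4.10 = +3.10 |
| 15% | 30 | 170 | -1.0 | -1 + 6.15 = +5.15 |

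**Where the sign changes.** Setting -1 + 41m = 0 gives m = 1/41 = 2.44%, or 200/41 = 4.9, about 5 deaths in 200.

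**Sensitivity to the assumed inputs.** In general m* = -s / (42 - b - s).
- s = -1: b = 1 gives 1/42 = 2.4%; b = 4 gives 1/39 = 2.6%.
- s = -0.5: b = 1 gives 0.5/41.5 = 1.2%; b = 4 gives 0.5/38.5 = 1.3%.

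Each death adds about 40 points to the sum, so the bound is driven almost wholly by the choice of 42. What does not depend on that choice is the fourth column: the survivor-only mean does not respond to the number of deaths.

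**The case against.** The strongest reply is that deaths are not lost from the study. The mRS comparison, with death as 6, stands in the same section and is made at the follow-up intervals. New neurological deficit and procedure-related complications are separate secondary endpoints. Death is a serious adverse event, and deaths go to the IRB within 10 days. The NIHSS comparison is itself secondary, and the plan is silent on deaths rather than stating that they are excluded. All of this stands, and it confines the point to the NIHSS analysis and to which scale carries the functional conclusion.

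Three stronger readings are tempting, and the documents do not support them.

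- **A harmful procedure could look beneficial overall.** A reader might infer this from the survivor-only mean. It could be true of the NIHSS line alone. It does not follow for the plan as a whole, because of the other measures just listed.
- **The NIHSS sits at its floor at entry.** A reader might infer this from the entry criterion "Minimal symptoms such as headache, altered mental status, or mild neurological deficit only" and the exclusion "Significant midline shift and/or neurologic symptoms requiring urgent decompression". Low baseline scores are plausible, but no baseline NIHSS or cut-off is given, altered mental status is allowed, and the Groups section adds poor surgical candidates with an 'or'. A floor would in any case limit measurable improvement, leave nearly the whole scale for worsening, and have no bearing on how deaths are handled.
- **The sign of the result would flip.** This rests on assumed inputs and on scoring death as 42. At 2% mortality with the inputs above it does not flip.

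It can also be said that Risks excludes patients whose comorbidities raise procedural risk. That may lower mortality, but ASA Class 4 or greater remains a named route into the study.

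The planned chi-square does not fully answer the point either. It has no stated deciding time point and no baseline adjustment, an ordinary chi-square ignores the order of the mRS levels, and the text does not rest the functional conclusion on it.

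**Conclusion.** The point holds in a limited form. The analysis that the plan assigns to functional outcome has no value and no rule for death, so followed as written it describes assessed survivors. The plan already contains a scale that avoids this, but does not give it the conclusion.

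The size of any distortion is unknown, because mortality and the NIHSS distribution are not in the documents. Under the assumed inputs, the gap between the survivor-only mean and the worst-score bound is 41m: 0.82 points at 2% mortality, 2.05 at 5% and 4.10 at 10%. That shows how sensitive the measure is to the missing rule and does not predict the trial's result.

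The change should be made, since it gives a less biased functional conclusion at little cost. It concerns a secondary endpoint and does not touch the primary comparisons.

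**What to change.** Amend the Statistical Analysis section before outcome data are examined.

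1. Name day-90 mRS, with deaths kept as 6, as the functional outcome. Adjust for baseline mRS where it is available, with a method that respects the order of the levels.
2. Keep NIHSS as a supporting measure of impairment. Either report the proportion worsened by a fixed, prespecified amount, counting death as worsened, or give deaths the worst rank and use a rank-based test.
3. State the time point and comparator for the NIHSS analysis, and report the number of deaths beside it.
4. If a mean NIHSS change is still shown, label it as applying to assessed survivors. Any version that scores death as 42 should be marked as a sensitivity bound.

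**Cost.** For embolized patients this changes analysis wording only, because both scales are already scheduled before the procedure and at 30 and 90 days. For the 400 controls from retrospective chart review, nothing in the plan shows that baseline and day-90 mRS exist. Their availability has to be confirmed before a baseline-adjusted comparison with controls is promised. The NIHSS result may look less favourable once deaths are counted.

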information gathered, time frame of participation, potential benefits, and risks of participation, including the risks of undergoing an interventional neuroradiology procedure. Treatment with middle meningeal artery embolization will be offered in addition to the standard surgical evacuation or observation by the physician in consideration of the patient's medical history and current condition. If patients are unable to provide informed consent, consent from the next of kin will be obtained in accordance with Missouri Statute Title XXVII, Section 431.064.

Patients will have as much time as they desire to think about the study, ask questions, and discuss with family. Any patient requiring emergent intervention or experiencing sudden neurologic deterioration is excluded from this study. The consent documentation contains a statement that consent is freely given, that the patient understands the potential risks and benefits of entering the study, and that the patient is free to withdraw from the study at any time. As the patient may experience a direct benefit from the study, the patient must initial yes/no to permission for future use of their data per policy. Patients who agree will then sign the IRB approved consent form prior to undergoing the procedure. The original signed consent will be maintained in a binder in a locked office. A copy will be given to the patient, with contact numbers if the patient has further questions or wishes to withdraw their consent. The expected duration of patient participation in the study is 90 days.

Based on a review of prior literature, we expect an effect size of 20% patients to meet the endpoint of recurrent or refractory subdural hematoma requiring surgery. With the addition of MMA embolization, we expect that only 5% of patients will meet this outcome. With equal numbers of patients in each arm, we estimate that 124 patients will be needed for a power of 80% using a two tailed alpha set at 0.5. In order to account for study dropout, we plan to study 200 patients who undergo MMA embolization. These patients will be compared to an additional 400 historical matched controls obtained via retrospective chart review from January 1st 2014 to December 31st 2018.

Inclusion/Exclusion Criteria

Must meet the following criteria for inclusion to undergo MMA embolization:

1. Patients 18 years or older undergoing treatment for a new diagnosis of chronic or acute subdural hematoma (cSDH)
or

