A serious adverse event (SAE) is any adverse event that results in one or more of the following outcomes:

- Death
- A life-threatening event
- Inpatient hospitalization or prolongation of existing hospitalization
- A persistent or significant disability/incapacity
- A congenital anomaly or birth defect
- An important medical event based upon appropriate medical judgment

AEs will be labeled according to severity, which is based on their impact on the patient. An AE will be termed “mild” if it does not have a major impact on the patient, “moderate” if it causes the patient some minor inconvenience, and “severe” if it causes a substantial disruption to the patient’s well-being. AEs will be categorized according to the likelihood that they are related to the study intervention. Specifically, they will be labeled definitely unrelated, definitely related, probably related, or possibly related to the study intervention.

Unanticipated events and deaths will be reported to the IRB within 10 days per institutional policy. Individual adverse events will be summarized and reported at continuing review without any subject level identifiable information. Any updates to study risks or benefits based on analysis of this study data or other new published research will be reported as a modification during continual review and may require updated consent. Determination of severity, SAE, and

unexpected event status will be decided by the PI. Adverse event documentation will be prepared and compiled by the research coordinator utilizing a standardized WUSTL reporting template.

Risks

Conventional burr hole craniotomy has a literature reported complication rate of 9%. The meta-analysis of middle meningeal artery embolizations demonstrated a composite complication rate of 2.1% in double arm studies²¹, especially significant as a greater proportion of embolization patients are maintained on anticoagulant medications. The largest individual study to date included 60 embolizations with no procedural related complications¹⁵. A meta-analysis including 15 studies with 193 procedures additionally reported no procedure-related complications²⁵.

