Expected risks to the subject due to the interventional procedure are minor pain and bruising at the catheter insertion site. About 5% of subjects may develop a hematoma, a collection of blood that may cause more bruising and pain than normal and may require intervention. Less likely, more serious risks of embolization procedures (<1%) include temporary neurologic deficits, blindness or cranial nerve palsy, or an anaphylactic reaction to the contrast dye.

There is a small risk (0.3%) of carotid artery dissection and/or stroke with permanent neurologic deficit from catheter injury or clot formation. Arterial perforation or brain hemorrhage is a life threatening but rare complication. Insertion site infection is exceedingly rare.

When procedures are performed through the radial artery, a combination of medications are used to prevent radial artery occlusion, which may be asymptomatic or may cause hand ischemia and the loss of the hand. Radial subjects receive a TR band at the conclusion of the procedure to maintain patent hemostasis. Radial artery occlusion is rare with these prevention measures. Femoral access subjects receive manual compression or a closure device and must be maintained on strict bedrest for 6 hours to prevent hematoma formation.

These risks are addressed in the consent form and are considered to be minimal or outweighed by the risk of multiple invasive surgical procedures or the risk to the patient by reaccumulation of the hematoma. Patients with known contraindications to angiography or comorbid conditions placing them at higher risk of procedural complications are excluded from study participation. The neurointerventional radiology department at BJH is a high volume center with experienced physicians and staff. Approximately 1200 outpatient diagnostic cerebral angiograms are performed each year and over 300 interventional procedures.

Study subjects will be followed for research purposes for 90 days and may continue long term follow up with their outpatient neurosurgeon. Study follow up visits occur at 30 days (± 7) post procedure, and 90(± 10) days post procedure. At each of these time points the subject will receive a head CT scan, neurologic assessment, and assessment of adverse events. Adherence to follow up visits will be tracked and reported.

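### The safety test compares complications tracked prospectively after embolization with complications read from 2014–2018 surgical charts, with no common definition, time window or attribution rule.

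*Combined protocol and SAP*

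**What the plan says.** **The comparison.** The Statistical Analysis section commits to a direct test: "the rate of procedure-related complications between embolized patients and surgical controls will be compared by t-test". Procedure-related complications are a listed secondary endpoint (Endpoints), and safety is part of Specific Aim 2.

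**Embolized patients.** The sample is prospective: "we plan to study 200 patients who undergo MMA embolization" (Participants). Study Procedure says: "Patients will be followed post-procedure for 90 days to track any complications or recurrence/persistence of the subdural hematoma". The Safety Monitoring Plan adds inpatient monitoring for at least 24–48 hours, and history and examination at baseline and follow-up to look for AEs. For the day-30 and day-90 visits, the Risks section says: "At each of these time points the subject will receive a head CT scan, neurologic assessment, and assessment of adverse events". Under Adverse Events, events are sorted by relatedness: "they will be labeled definitely unrelated, definitely related, probably related, or possibly related to the study intervention".

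**Surgical controls.** These are group 4 under Groups, "Surgery Alone (Historical Cohort", and belong to "an additional 400 historical matched controls obtained via retrospective chart review from January 1st 2014 to December 31st 2018" (Participants). How many of the 400 are surgical is not stated.

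**What is absent.** No section defines a procedure-related complication, lists the events that qualify, gives a time window for the comparison, or says how an event is found or attributed in a control chart.

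**The concern.** A difference between two complication rates can be read as a safety difference only if both are counted in the same way. Here one group is seen at scheduled visits where AEs are looked for. The other is known only through notes written for clinical care, years before the study.

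The two influences can pull in opposite directions. Active search tends to raise the embolized rate relative to the chart rate. Unblinded judgement of relatedness, if it decides which events count, could lower it. The plan gives no means of separating either influence from a true difference. The test could show a harm signal that is only surveillance, or miss a real advantage of embolization.

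**Working it through.** **Step 1: the counting rules side by side.**

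| | Embolized patients | Surgical controls |
|---|---|---|
| Data source | Prospective follow-up (Study Procedure) | Chart review, 2014–2018 (Participants) |
| Scheduled AE assessment | Days 30 and 90 (Risks) | None possible |
| AE definition | Events during study participation (Adverse Events) | Cannot apply as written |
| Relatedness scale | To the study intervention (Adverse Events) | Cannot apply as written |
| Definition of the compared endpoint | None stated | None stated |
| Window for the compared endpoint | 90 days of tracking, not tied to the endpoint | None stated |

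**Step 2: inputs for an illustration.** The plan gives no sample size, alpha, power or expected difference for the safety test, so there is no stated figure to reproduce.
- From the documents: 200 embolized patients; at most 400 surgical controls; complication rates of 2.1% for embolization and 4.4% for conventional treatment (Prior Research); 9% for burr hole surgery (Risks).
- Assumed: all 400 controls are surgical (an upper bound); two-sided 5% test; every event found in embolized patients; a share *s* of events found in charts, taken as 100%, 75% or 50%.

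**Step 3: formula.** Let p1 be the observed embolized rate and p2 = *s* × the true surgical rate.
- Pooled rate: pb = (200·p1 + 400·p2)/600
- Null standard error: SE0 = √[pb(1 − pb)(1/200 + 1/400)]
- Actual standard error: SE1 = √[p1(1 − p1)/200 + p2(1 − p2)/400]
- With d = p1 − p2 and c = 1.96·SE0, the probability of rejection is 1 − Φ((c − d)/SE1) + Φ((−c − d)/SE1).

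**Step 4: one case in full.** True rate 4.4% in both groups, *s* = 50%.
- p1 = 0.044, p2 = 0.022, d = 0.022
- pb = (8.8 + 8.8)/600 = 0.0293
- SE0 = 0.0146, c = 0.0286, SE1 = 0.0163
- Rejection = 1 − Φ(0.409) + Φ(−3.116) = 0.341 + 0.001 = 34.2%

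**Step 5: chance of a false difference when true rates are equal.**

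| True rate in both groups | Charts find 100% | 75% | 50% |
|---|---|---|---|
| 2.1% | 5% | 8.7% | 20.6% |
| 4.4% | 5% | 11.6% | 34.2% |
| 9% | 5% | 17.8% | 58.2% |

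With 200 surgical controls instead of 400, the 75% and 50% columns become 6.8% and 13.4% (at 2.1%), 8.8% and 23.3% (at 4.4%), and 13.3% and 43.4% (at 9%).

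**Step 6: loss of power when embolization is truly safer.** With true rates of 2.1% and 9% and 200 vs 400, power is 93.5% at full chart capture, 70.8% at 75% (observed 2.1% vs 6.75%) and 29.0% at 50% (observed 2.1% vs 4.5%).

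**Step 7: the opposite direction.** Suppose both true rates are 5% and charts are complete, but only 75% (50%) of events in embolized patients are labelled related and counted. The observed rates are then 3.75% (2.5%) vs 5%, and the chance of a false difference in favour of embolization is 9.2% (28.3%).

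The normal approximation is rough at the lowest rates: 2.1% of 200 is about 4 events. The pattern matters more than the decimals.

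**The case against.** The strongest reply is that the plan does not state two different counting rules. The AE text sits in the safety monitoring part of the document, and no section says that it feeds the compared endpoint. The data tables carry a procedural-complications column in the initial data, while the follow-up table has no AE or complication column. A reader might infer that the relatedness scale decides which embolization events are counted; the documents do not say so. This stands, and it moves the fault to the absence of any common rule. It does not remove the fault. The complications column has no definition, and its table is keyed to a study number assigned at consent, which historical controls do not have. Study Procedure also ties the 90-day follow-up to tracking complications.

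Three further inferences are tempting and unsupported:
- *Minor events are caught in one group only.* The plan says only that controls come from chart review, and charts may hold some minor events. Catheter-site events are also partly a real difference between the procedures, since surgery alone has no catheter site.
- *The investigators' own team attributes the events.* Under Adverse Events the principal investigator decides severity, seriousness and unexpectedness, but the assessor of relatedness is not named. AEs also go to departmental and institutional quality committees (Safety and Analysis).
- *Under-recording reverses the result.* Adding the expected 5% access-site hematoma to the 2.1% composite gives 7.1%. Against half of 9%, which is 4.5%, embolization looks worse; against the full 9% it looks better. But the sum may double count, and reversal needs chart capture below 7.1/9 = 79% (below 5/9 = 56% if 5% is used alone). With 4.4% for surgery, 7.1% is already higher at full capture, so nothing reverses. With 2.1% vs 9%, half capture still leaves 2.1% vs 4.5%.

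It is also fair to say that unequal ascertainment comes with any historical-control design and that this is a secondary endpoint. Here, though, no part of the plan reduces the problem, and wording can remove much of it.

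**Conclusion.** The concern holds in this form: the plan tests a prospectively tracked complication rate against a chart-derived one with no shared definition, window or attribution rule, so the difference mixes ascertainment with safety. The net direction cannot be determined from the documents.

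On the stated assumptions, 75% chart capture raises the chance of a false difference from 5% to between 8.7% and 17.8%, and 50% capture raises it to between 20.6% and 58.2%, depending on the true rate. A true advantage of 2.1% vs 9% would be detected with 70.8% or 29.0% power instead of 93.5%. The capture shares, the 5% alpha and the 400 surgical controls are assumptions, so these figures show sensitivity and do not forecast the result. The asymmetry itself rests on the documents alone. The plan should be changed, with weight proportionate to a secondary safety endpoint.

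**What to change.** In the Statistical Analysis section, define the compared safety endpoint as one fixed list of events that routine charts record reliably, counted regardless of attribution:
- death;
- stroke or new deficit documented in routine care;
- new intracranial hemorrhage;
- infection needing treatment;
- access-site or wound event needing intervention;
- seizure;
- unplanned readmission.

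Count these within one window, for example 30 days, from an index procedure defined for each group. For group 2, who may have an evacuation and then an embolization in the same admission, state which of the two starts the clock. Abstract the events from the routine clinical record in both groups with the same form, so that a deficit found only at a study visit does not enter the comparison.

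Keep re-operation for hematoma out of the list, because it is already a primary endpoint. Report all other AEs, including those found only at study visits, descriptively for embolized patients. Since events count regardless of attribution, the comparison needs no relatedness adjudication.

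Cost: SAP wording, one abstraction form and a little more abstraction work, because embolized patients' routine records must be abstracted too. No new visits are needed. Minor events leave the between-group comparison but are still reported. Changing only the t-test would leave this problem in place.
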